9. RESEARCH METHODS

9.1 STUDY DESIGN

This is an observational cohort study based on existing data.

BOEHRINGER INGELHEIM Group of Companies**NIS Protocol Template****Study number: 1484.0014****Page 12 of 30****Document number: <insert>****9.1.1 Study population**

Study inclusion criteria: All patients ≥ 50 years, with a GA diagnosis in at least one eye, including in the [REDACTED] database identified during the study period (January 2015 to April 2023).

Exclusion criteria: Patients without the information of laterality will be excluded.

No other exclusion criteria are applied for the identification of the study population and description of the patients and eye at baseline.

Additional note:

For certain analysis the patient population will be restricted to those with at least 12, 24, 36, 48, or 60 months of history following diagnosis of GA. For the analysis requiring a VA reading, a restriction to those patients with valid VA readings at the index diagnosis and the respective follow-up times will be applied.

For analysis estimating the size of the GA population relative to other retinal diseases, the same timeframe requirements that the study population will be applied. In this population, any patient in the database will be eligible, and the diagnosis of DME, DR or other conditions may be used for subgroup comparisons.

Primary Disease Definitions

In the [REDACTED] Database, retinal and other diseases are identified using the International Classification of Diseases (ICD), Tenth Revision, Clinical Modification. ICD 10 codes were launched in the USA in October 2015, and are the only version of ICD codes with adequate descriptions of GA and dry AMD severity. As such, only ICD 10 codes will be analyzed in this study and the study period defined above is directly related to the launch of ICD 10 plus a small buffer allowing for physician familiarity.

These codes are entered by the physician at patient visit, with an associated laterality. This, along with the ICD 10 laterality is used in combination to confirm in which eye the disease is occurring. For this study, a patient eye will be considered to have the study disease so long as there is an accompanying ICD code. The primary study diseases to be analyzed are dry AMD, GA and wAMD, and will be identified using the ICD codes in Table 1 below.

Table 1. Study disease definitions-codes.

Study Disease Definitions			
	Dry AMD*	Dry AMD with GA*	wAMD*

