ICD 10	H35.311X, H35.312X, H35.313X, H35.319X	H35.3113, H35.3114, H35.3123, H35.3124, H35.3133, H35.3134, H35.3193, H35.3194	H35.321X, H35.322X, H35.323X, H35.329X
ICD 9 (2015 only)	362.51	N/A	362.52

*a comprehensive list of all AMD ICD codes is included in the Appendix

BOEHRINGER INGELHEIM Group of Companies**NIS Protocol Template****Study number: 1484.0014****Page 13 of 30****Document number: <insert>**

Patients could have simultaneously a diagnosis of wAMD and GA in the same eye. If both conditions are present, wAMD will be described as part of the comorbidities of the study or fellow eye. Patients could also have other ocular comorbidities affecting VA (section 9.3.3), those will be described and for the progression analysis will be analyzed separately.

For the follow-up analysis in the study eye or fellow eye, results will be described for all GA patients, patients with GA and wAMD, and patients with patients with GA only (without wAMD or other ocular comorbidities).

As the progression analysis tracking multiple different metrics across 2 eyes, it will be conducted at the patient level. Bilateral AMD disease is quite common (and will be identified), therefore the following methodology will be used to identify the 'Study' (primary) eye and the 'Fellow' (secondary) eye:

Study Eye – The first study eye in patient history identified with GA in the [REDACTED] database. GA is the only identifying disease in this case, and wAMD or dry AMD (without GA) in the study eye is not taken into account for study eye definition. If patients are bilaterally diagnosed, the study eye will be selected at random.

Fellow Eye – is defined as the other eye in a patient having their study eye diagnosed with GA. The fellow eye can have dry AMD, wAMD, GA or other retinal conditions. The fellow eye will be followed for progression purposes throughout the study.

Disease Status

Patient eyes will be identified at every visit throughout the study period to estimate the first time occurrence of GA and to estimate the proportion of patient with the disease over the years of the study period. Each visit will be classified as either an incident or a prevalent visit, defined below:

Incident visit – The first visit in patient eye history identified with GA in the [REDACTED] database. This timepoint also acts as each patients' index diagnosis. The incident visit may only occur once and contribute to one calendar year.

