9.7 DATA ANALYSIS

9.7.1 Main analysis

All analysis will be performed individually on the study population(s). All study results will be provided in tables, and key findings will be highlighted and summarized. The analyses will be conducted at both the patient and patient eye level, as appropriate.

Analysis for objective:

To describe the characteristics* of patients with GA in at least one eye.

To describe characteristics* of the study eye and the fellow eye, at index diagnosis (i.e., proportion of patients with GA in the fellow eye, [REDACTED]

All demographics, and clinical characteristics will be summarized at the index diagnosis date (first diagnosis of GA in the study eye).

Characteristics include demographics, comorbidities, comedications (patient level).

And at eye level; AMD, GA, eCNV, other ocular comorbidities, functional parameters i.e. VA. As well as treatments administered prior to or at index.

Summary will include descriptive statistics; continuous variables will consist of mean (SD) and median (IQR) while categorical variables will be described using frequency and proportion. Absolute numbers (n) of the variables (either yes or patients as appropriate) will be always included in the description of the results.

Analysis for objective:

To evaluate and characterize the progression of newly diagnosed patients with GA during a 5-year follow-up period. To describe patients' characteristics, study eye and the fellow eye characteristics, [REDACTED]

[REDACTED] or progression of the GA lesion in the study eye. To evaluate changes in VA, to evaluate changes in the lesion location, and lesion size (where available).

Patients with GA will be analyzed as an overall group. Subgroups will be also analyzed separately: only GA, GA and wAMD, GA and other comorbidities, and bilateral GA at baseline.

Ocular comorbidities will also be tracked longitudinally (yearly) from index date (GA diagnosis in the database) to better understand the disease journey.

Disease progression will be analyzed at both patient and each individual eye level.

Progression to dry AMD, to GA and to wAMD will be assessed independently using time to event analysis, and also the rate of progression that is seen in the study (2nd, 3rd, 4th, and 5th) years. Bilateral GA eyes at baseline will be evaluated for progression to wAMD

BOEHRINGER INGELHEIM Group of Companies**NIS Protocol Template****Study number: 1484.0014****Page 23 of 30****Document number: <insert>**

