An additional analysis will be made to extrapolate the prevalent results to a national – US-level. For that analysis, the prevalence of GA will be considering all patients seen by a retina specialist in the given year. With this metric, estimation on a national level will be done using an estimation of all practicing US retina specialists.

When analyzing the rate of progression from dry AMD to GA, a conversion analysis will be done. This will include the overall rate of dry AMD eyes developing GA, along with a Kaplan Meier analysis assessing the rate of conversion over time. This analysis will track progression by month from diagnosis, censor any patient at the final visit in the database, and identify the incident GA diagnosis as an event.

Analysis for objectives:

To evaluate patients' management (i.e. patients visits and procedures) over the study period.

BOEHRINGER INGELHEIM Group of Companies**NIS Protocol Template****Page 24 of 30****Study number: 1484.0014****Document number: <insert>****Patients' management**

All visits, treatment, checkups, procedures, and other will be summarized across the duration of the study time frame as well as between the index diagnosis and at the 12 (24, 36, 48, 60) month follow up period.

An additional sub analysis will be conducted to evaluate the changes in the frequency of patients visits or procedures, checkups, after the third quarter of 2021 and after [REDACTED].

Summary will include descriptive statistics; continuous variables will be described by absolute numbers, the mean (SD), median and range, while categorical variables will be described using frequency and proportion. Absolute numbers (n), and correspondent percentage (%) of the variables (either eyes or patients as appropriate) will be always included in the description of the results.

Analysis for objective:

To describe and compare patients' characteristics in different progression subgroups (i.e. those that develop eCNV/those that not), of the overall GA population.

The following groups will be evaluated to better understand progression:

1. Patients that [REDACTED]

vs. those that do not in the 1, 2, 3, 4 and 5 years of follow up period.

2. Patients that [REDACTED]

vs. those that do not in the 1, 2, 3, 4 and 5 years of follow up period.

3. Patients with subfoveal lesion location vs. those with extrafoveal lesion location.

For this subgroup of patient's characteristics will be described and compared.

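### The curve labelled dry AMD-to-GA progression pools direct conversion with GA coded after wAMD; the two routes should be reported separately

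*Combined protocol and SAP*

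**What the plan says.** Section 9.7.1 deals with conversion to GA in two places.

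- **Progression of newly diagnosed GA patients:** "Progression to dry AMD, to GA and to wAMD will be assessed independently using time to event analysis". The study eye already has GA here, so conversion to GA concerns the fellow eye. Section 9.3.2.1 lists development of GA as a fellow-eye endpoint.
- **Occurrence of GA:** "When analyzing the rate of progression from dry AMD to GA, a conversion analysis will be done". It is described further: "This will include the overall rate of dry AMD eyes developing GA". A monthly Kaplan-Meier analysis follows, which is to "censor any patient at the final visit in the database, and identify the incident GA diagnosis as an event".

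Section 9.1.1 sets out how eyes are classified.

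- An eye has a disease by code alone: "a patient eye will be considered to have the study disease so long as there is an accompanying ICD code".
- "Patients could have simultaneously a diagnosis of wAMD and GA in the same eye"; in that case wAMD is described as a comorbidity.
- "The fellow eye can have dry AMD, wAMD, GA or other retinal conditions", and it is followed for progression throughout.
- Apart from missing laterality, "No other exclusion criteria are applied for the identification of the study population". That sentence governs the GA population. No separate entry rule is given for the dry AMD eyes in the conversion analysis.

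Sections 9.1.1 and 9.7.1 also plan results for GA patients with and without wAMD.

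**The concern.** The censoring rule is complete as written, and wAMD appears in it neither as an exclusion, nor as a censoring point, a competing event or an intermediate state. An eye that develops wAMD stays in the dry AMD risk set, and a later GA code counts as conversion from dry AMD. Section 7 calls wAMD another advanced form of AMD with its own treatment, so GA reached from there is a different transition.

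Coding adds uncertainty. In Table 1, GA exists only within the dry AMD code family, and wAMD has a separate family. GA in a wAMD eye is recorded only if the physician also enters a dry AMD code with GA. Depending on habit, such eyes either add events or stay in the denominator with little chance of an event.

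Conversion in both eyes is the central question of the study. A reader will take the curve as the risk of GA arising from dry AMD, and the curve does not isolate that.

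**Working it through.** **Inputs.** The documents give no GA rate in dry AMD eyes, no wAMD rate in such eyes and no GA rate after wAMD, so there is no planned figure to reproduce. The only wAMD figure is 20 to 40% in section 7; it comes from GA trials and covers wAMD in the fellow eye or conversion to it. Every rate below is an assumption.

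**Model.** Constant hazards: λ for GA without wAMD, μ for wAMD, kλ for GA after wAMD. Time t = 5 years.

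- GA without prior wAMD (what Aalen-Johansen estimates): λ/(λ+μ) × (1 − e^(−(λ+μ)t)).
- Eyes with wAMD and no GA: μ/(kλ−λ−μ) × (e^(−(λ+μ)t) − e^(−kλt)).
- Planned curve (any GA), if loss to follow-up is unrelated to wAMD: 1 − e^(−(λ+μ)t) − the previous line.

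**Step 1: λ = μ = 0.03 per year, no wAMD at entry.** Here e^(−0.30) = 0.7408.

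- GA without prior wAMD: 0.5 × (1 − 0.7408) = 13.0%.
- k = 1: wAMD without GA = 0.8607 − 0.7408 = 0.1199. Planned curve = 1 − 0.7408 − 0.1199 = 13.9%. The gap is just under 1 point, and 7% of events come after wAMD.
- k = 3: wAMD without GA = 0.7408 − 0.6376 = 0.1032. Planned curve = 15.6%, with 17% of events after wAMD.
- k = 0 (GA never coded after wAMD): planned curve = 13.0%, no gap.

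**Step 2: five-year direct GA risk 20%, five-year wAMD risk 20% or 40%, no wAMD at entry.** λ = −ln(0.8)/5 = 0.0446; μ = 0.0446 or −ln(0.6)/5 = 0.1022. GA without prior wAMD is 0.5 × (1 − 0.64) = 18.0%, or 0.304 × (1 − 0.48) = 15.8%.

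| k | Planned, wAMD 20% | Events after wAMD | Planned, wAMD 40% | Events after wAMD |
|---|---|---|---|---|
| 0.5 | 19.0% | 5.5% | 18.0% | 12.1% |
| 1 | 20.0% | 10.0% | 20.0% | 21.0% |
| 2 | 21.7% | 17.1% | 23.6% | 33.0% |
| 3 | 23.2% | 22.4% | 26.7% | 40.7% |

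At k = 1 the planned curve equals the Kaplan-Meier censored at wAMD, yet 10 to 21% of its events still come through wAMD.

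**Step 3: wAMD at entry.** If 10% of eyes carry wAMD at entry, direct GA risk is 10 or 20%, wAMD risk is 20 or 40% and k runs from 0.5 to 3, then 11 to 53% of events follow wAMD. With none at entry the range is 5.5 to 43%.

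**Step 4: unequal loss.** The planned curve becomes 1 − exp(−∫h), with h = λ(1 + (k−1)s) and s the wAMD share of eyes at risk. Take the rates of step 1, with loss hazards of 0.50 per year before wAMD and 0.15 after. The curve is then 12.2% (k = 0), 13.9% (k = 1) and 16.8% (k = 3), against 13.0%. The wAMD share at year 5 is 27 to 33%, compared with 12 to 15% if loss is 0.50 in both states.

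**The case against.** The strongest reply is that any GA is a legitimate target. wAMD does not prevent GA, the protocol allows both in one eye and chooses to describe wAMD as a comorbidity, and the text speaks of the overall rate at which dry AMD eyes develop GA. Counting every first GA code and censoring at the last visit is the standard estimator for that. This stands, and so the planned curve should be kept. The reply does not settle the label, which promises progression from dry AMD, or the absence of any split by route.

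Three further points narrow the issue.

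- A reader might infer from the word *independently* that the plan assumes the endpoints are statistically independent. The sentence can equally mean that each endpoint is analysed on its own. The point rests on the event and censoring rule.
- A reader might infer that every wAMD eye enters the risk set. Table 1 separates the code families, so an eye coded only as wAMD is not clearly a dry AMD eye. The entry problem is limited to eyes with both codes and to fellow eyes. Part of the fellow-eye endpoint text is redacted, so that reading is less certain.
- The GA-only and GA-with-wAMD subgroups help in part. They classify patients who already have GA; they neither define the dry AMD risk set by wAMD status nor order the two codes.

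The study is also descriptive, with no hypothesis test or sample size resting on this curve.

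**Conclusion.** The point holds as a mismatch between label and estimand. The rule pools direct conversion with GA coded after wAMD, and nothing else in the plan separates them.

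Its size is unknown. Under the assumed constant hazards the difference is under 1 point at equal hazards of 3% per year. It reaches several points when the GA hazard after wAMD is higher or wAMD is common: 26.7% against 15.8% in the most extreme row of the table.

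A reader might infer a large bias in a known direction, and the documents do not support that. With no wAMD at entry and equal loss, the planned figure is at or above the direct one. It falls below (12.2% against 13.0%) if GA goes uncoded after wAMD and wAMD eyes are kept longer.

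The loss rates in step 4 are not calibrated. A hazard of 0.50 with administrative censoring uniform over 7.5 years gives 0.223 × 0.6 = 13% of eyes followed beyond 3 years. Section 9.5 reports 20,503/72,718 = 28% of patients with visits after 3 years, though these are GA patients.

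This is a cheap improvement to an otherwise usable analysis.

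**What to change.** In section 9.7.1, for conversion to GA in dry AMD eyes and in fellow eyes:

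1. Enter only eyes with no wAMD code on or before time zero.
2. Report the cumulative incidence of GA without prior wAMD (Aalen-Johansen), with the first wAMD code in that eye as a competing event, as the dry AMD-to-GA result.
3. Report GA after wAMD on a separate line.
4. Keep the planned Kaplan-Meier curve as a supplement labelled *any GA, with or without prior wAMD*.
5. Reword the sentence on independent assessment to match.

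The cost is a few sentences of protocol text and a standard estimator applied to codes already extracted. Eyes with wAMD at entry leave this one analysis, and the count of direct conversions is somewhat smaller than the pooled count.

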Population:	
Patients attending a retina specialist, contributing to the [REDACTED] Database. Patients will be identified in the database from January 1, 2015, to April 30, 2023.
 
From those, our study population will be patients ≥ 50 years with a GA diagnosis in at least one eye will be eligible for this study.
 
The study period was selected to be able to identify patients with GA using the ICD-10 codes introduced in that year. The period from January 2015 until October 1st, 2015 will be used to identify patients diagnosed with ICD-9 codes and further classify them as new cases or patients with an previous diagnoses.
		
Variables:	
A primary outcome variable is visual acuity (VA), reported using converted Early Treatment Diabetic Retinopathy Study (ETDRS) letters.
 
[REDACTED]
 
[REDACTED]
 
[REDACTED]
 
Demographic characteristics – including age, gender, patient history, visit history
 
Clinical Characteristics – including ocular comorbidities, lens status, systemic conditions
		
Data sources:	
The [REDACTED] database consists of de-identified Electronic Health Records from a geographically diverse panel of 360+ United States based private retinal specialists contributing data from 70+ practices. Over the datasets entire history, there have been about 2 million patients and about 13 million patient visits.
		

BOEHRINGER INGELHEIM Group of Companies

NIS Protocol Template

Page 9 of 30

Study number: 1484.0014

Document number: <insert>

Study size:	
All patients available in the database and meeting the study criteria will be included.
 
The [REDACTED] includes approximately 400,000 patient eyes diagnosed with dry AMD, and around 70,000 patients diagnosed with GA during the study period. After the initial feasibility analysis, it is expected, given the study criteria, that there will be around 100,000 eyes included. However, this number might change in the final analysis.
									

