9.3.3 Covariates

9.3.3.1 Demographic Characteristics: The demographic variables below are identified at the patient eye level and will be used to describe the demographic characteristics throughout the analysis. These demographic characteristics will be analyzed at the index diagnosis, unless specified elsewhere.

Age: will be calculated based on DOB from index diagnosis (incident visit).

Sex: identified at index diagnosis, or other visits if not specified.

Diagnosis year: Identified as the calendar year of the index diagnosis.

Months of History: will be defined as the time from index diagnosis to their last record in the database.

Incident Visit: The first visit in the database where one of the study diseases is identified, per eye. This may include Dry AMD, GA and/or wAMD. At incident visits all clinical characteristics, ocular comorbidities, etc. will be also captured.

Prevalent Visit: The first visit during a time period of interest where one of the study diseases is identified, per eye. This may include Dry AMD, GA and/or wAMD. This visit must not be the first diagnosis in the entire patient history. At prevalent visits changes in the clinical

BOEHRINGER INGELHEIM Group of Companies**NIS Protocol Template****Study number: 1484.0014****Page 19 of 30****Document number: <insert>**

characteristics, ocular comorbidities will be captured and described based on the first prevalent visit per calendar year.

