For all time to event metrics, mean (SD), median and range will be summarized, while proportions will be summarized using N (%).

Kaplan Meier or Cox Hazard ratios may be applied when analyzing disease progression. Additionally, it will be determined how patients progress during the 1,2,3,4,5 years follow up according to the lesion location, and lesion size.

Analysis for objective:

To determine the occurrence of GA in the study eye during the study period (at the 12 (24, 36, 48, 60) month follow up period).

The calculation of the occurrence (new cases) of GA will be tracked against the overall number of patients included in the retinal specialist database (████████ database) in a time period (year) as the denominator initially.

The analysis to calculate the prevalent cases will include all patients with a GA diagnosis active in the database in the given time period in the numerator, and all patients included in the retinal specialist database (████████ database) will be used as the denominator initially.

Since, this analysis is referring to a population attending a retinal specialist during a given time period and therefore is not a general population-based estimates, in order to give a context to the data, the proportion of other common diagnosis in patients over 50 years or older attending the clinic in the same time period (e.g. diabetic macular edema, diabetic retinopathy, proliferative diabetic retinopathy, and wAMD) will be calculated. The denominator will be all patients attending to the retina specialist in the given time period using the age group category that is applicable in this study (50 years or older).

For the initial calculations, the look back period in 2015 will be used to discard patients with prevalence GA diagnosis in the subsequent years. prior diagnosis will be excluded and only new cases diagnosis in the time period will be considered in the numerator when calculating incidence.

The calculations will be conducted by calendar year, and absolute numbers (n) and correspondent percentage (%) will be provided. As a sub analysis, it will be evaluated if changes occurred after the third quarter of 2021, corresponding with the ██████████

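### Code-based progression is dated at the first coded visit, so groups seen at different frequencies can differ in early progression and time to conversion with identical disease, and the plan has no check for this

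*Combined protocol and SAP*

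**What the plan says.** - **Event definition.** Section 9.1.1: "a patient eye will be considered to have the study disease so long as there is an accompanying ICD code". Section 9.3.3.1 defines the incident visit as "The first visit in the database where one of the study diseases is identified, per eye".
- **Event date and censoring.** The rule is spelled out only for the dry AMD to GA conversion analysis in 9.7.1, which will "censor any patient at the final visit in the database, and identify the incident GA diagnosis as an event". No other rule is given for the remaining code-based endpoints.
- **Method.** Section 9.7.1: "Progression to dry AMD, to GA and to wAMD will be assessed independently using time to event analysis". It adds: "Kaplan Meier or Cox Hazard ratios may be applied when analyzing disease progression". Mean and median time to conversion are also to be reported.
- **Visits.** Section 9.2.2 sets no visit plan. Section 9.3.2.2 counts every visit for both eyes, and gives treatment, check-up and sudden vision problems among the reasons for a visit.
- **Groups.** In 9.1.1, "results will be described for all GA patients, patients with GA and wAMD" and for patients with GA only. Section 9.7.1 adds GA with other comorbidities and bilateral GA at baseline.
- **Acknowledged bias.** Section 9.9 mentions more regular attendance only as a selection issue where a visual acuity or other key clinical reading is required. It offers Kaplan-Meier as a remedy for short follow-up. Visit counts are summarised as a patient-management outcome, not used to qualify the progression results.

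**The concern.** Progression happens between visits but is recorded at the next visit that carries the code. Right-censored Kaplan-Meier and Cox take that visit as the event date. A patient seen often has events dated close to onset, and a patient seen rarely has them dated months late. Because each visit counts for both eyes, an eye is observed more closely when its partner is under treatment.

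The endpoints exposed are those read from codes: GA in the fellow eye, wAMD in the fellow eye, change of GA location, and wAMD in the study eye when results are split by fellow-eye status. The last matters most. Section 7 gives as a reason for the study that conversion in the study eye may depend on wAMD in the fellow eye, and wAMD is the form that section 7 says can be treated with anti-VEGF. If patients with a treated fellow eye attend more often, detection timing alone could produce part of that pattern in the first year. With 113,408 eyes in the feasibility count (9.5), sampling error would not hide an artefact of this kind.

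**Working it through.** The plan states no event rate by group, visit interval or power figure to reproduce, so the check simulates its dating rule with the same true hazard in every group.

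**Inputs from the documents:** event at the first coded visit and censoring at the final visit (9.7.1, assumed to apply to all code-based endpoints); index date is itself a visit (9.1.1); average follow-up 22 months (9.5).

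**Assumptions:** hazard 10% per year; visit gaps varying between 0.5 and 1.5 times their mean; exponential follow-up with mean 22 months, capped at 60; complete coding at each visit.

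**True cumulative risk**, 1 − exp(−0.10 × years): 12 months, 1 − exp(−0.10) = 9.5%; 24 months, 1 − exp(−0.20) = 18.1%; 58 months, 1 − exp(−0.483) = 38.3%.

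**Kaplan-Meier under the plan's rule:**

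| | Visits every 1 month | Visits every 6 months | Ratio |
|---|---|---|---|
| 12 months | 9.4% | 7.9% | 9.4/7.9 = 1.19 |
| 24 months | 18.2% | 18.3% | 18.2/18.3 = 0.99 |
| near 58 months | 39% | 43% | 39/43 = 0.91 |
| Median time to conversion among converters | 12.6 months | 15.3 months | 2.7 months later |

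The gap closes and reverses because of censoring at the last visit. An eye with no further visit leaves the risk set at once. The eyes still at risk are those with another visit to come, at which a whole interval's events are counted.

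**Dependence on the visit interval.** A separate set of runs used a 24-month risk of 20%, which is a hazard of −ln(0.8)/2 = 0.112 per year. The 20% is the lower end of the 20 to 40% conversion in section 7, which gives no time horizon. Apparent Cox hazard ratios, often v rarely seen (truth 1.00):

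| Mean interval | To 12 months | To 24 months | To 60 months |
|---|---|---|---|
| 1 v 3 months | 1.07 | 1.03 | 1.01 |
| 1.5 v 6 months | 1.22 | 1.11 | 1.03 |
| 1 v 12 months | 2.34 | 1.26 | 1.07 |

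At a 24-month risk of 40% the 1 v 12 row becomes 2.51, 1.35 and 1.15. These ratios carry simulation error of a few hundredths. The mean dating delay is close to half the interval: 0.5, 1.6, 3.2 and about 6.3 months for visits every 1, 3, 6 and 12 months.

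**Dependence on coding** (1.5 v 6 months, hazard ratio to 60 months). With complete coding it is 1.02. If half the visits in both groups record the code, it rises to 1.22. If 25% of the frequent visits record it against 100% of the rare ones, it reverses to 0.79.

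**Interval-censored check.** Placing the event between the last visit without the code and the first visit with it, an exponential likelihood gives 0.099 to 0.102 per year in every group (truth 0.100). In the second set of runs the often/rare rate ratio is 0.98 to 1.02.

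**The case against.** The case against has real weight.

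- **Size and direction rest on inputs the plan does not give.** No section states visit or injection intervals by group. That patients with wAMD attend more often is an inference from their being treatable. At 1 v 3 months the effect is small. Section 9.9 says that physicians tend to leave out information not relevant to the present condition, so an injection visit may code only the treated disease, which could offset or reverse the direction. This stands, and it rules out stating the direction as fact.
- **The contrast is not a formal test.** The GA-only and GA-and-wAMD groups are described separately, and Cox is only optional. Study-eye conversion to wAMD is not open to eyes that already have it, and visual acuity is read in windows around fixed dates. This narrows the point to the endpoints listed above. It does not remove it, because the results will be read side by side.
- **A larger figure is tempting.** Counting cumulative detection without censoring, with visits at random phase, gives 9.2% v 7.3% at year 1 (ratio 1.26) and 17.8% v 16.1% at year 2 (1.11) for monthly v 6-monthly visits. A reader might infer a distortion lasting through year 2. That is not the Kaplan-Meier in the plan, which starts from an index visit and censors at the last one; there the gap is about nil by 24 months.
- **Interval censoring has its own assumptions.** It takes a code-free visit as evidence of no disease, yet 9.9 says that physicians tend not to enter null information. It also needs visits that are not prompted by progression, yet sudden vision problems are a listed reason. This stands against making it the primary method. It does not count against a sensitivity analysis, since the plan itself treats each visit as an assessment of both eyes.

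**Conclusion.** The point holds in a limited form. The dating rule, the absence of a visit schedule and the crediting of visits to both eyes are all in the protocol, and no planned analysis addresses visit frequency for code-based progression. With identical disease, visits every 1 v 6 months would give a 12-month Kaplan-Meier ratio of about 1.19 and shift the median time to conversion by about 2.7 months. The Kaplan-Meier difference is about nil at 24 months and reverses later. The effect is small at 1 v 3 months and large in year 1 at 1 v 12.

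These sizes depend on assumed intervals, an assumed hazard and complete coding. The documents do not support a claim that the GA-and-wAMD group will certainly appear to progress earlier, that five-year results are inflated in that direction, or that Kaplan-Meier must be replaced. They do support treating differences in early progression and time to conversion as uninterpretable until visit frequency is shown and a sensitivity analysis agrees.

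**What to change.** In 9.7.1:

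1. Keep Kaplan-Meier and Cox as planned.
2. Report the median visit interval for GA only, GA and wAMD, bilateral GA, and by wAMD status of the fellow eye.
3. For the code-based endpoints, add a sensitivity analysis that treats the event as interval-censored between the last visit without the code and the first visit with it: a Turnbull curve, and interval-censored proportional hazards for any group contrast.
4. State that subgroup differences in 12-month progression or time to conversion will not be read as disease differences unless they persist in that analysis.

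In 9.9, state that the sensitivity analysis assumes a code-free visit means no disease and that visits are not triggered by progression, so it reduces the bias rather than surely removing it.

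The cost is some extra programming in R, which the plan already uses, and wider intervals. Both visit dates are already in the visit-level data, so no new data are needed.
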